**Table 6 Case definitions for data analysis**

Case	At sea level up to 2500 meters elevation	Above 2500 meters elevation
RSV-RTI	Runny nose OR blocked nose OR cough AND Confirmed RSV infection 	Same
RSV-LRTI	History of cough OR difficulty breathing  AND SpO 2 < 95%  , OR RR increase  AND Confirmed RSV infection 	Same but with SpO2 < 92%
severe RSV-LRTI	Meeting the case definition of RSV-LRTI AND SpO 2 < 93%  , OR lower chest wall in-drawing	Same but with SpO2 < 90%
very severe RSV-LRTI	Meeting the case definition of RSV-LRTI AND SpO 2 < 90%  , OR inability to feed, OR failure to respond / unconscious	Same but with SpO2 < 88%
RSV hospitalization	Confirmed RSV infection  AND Hospitalized for acute medical condition 	Same
All-cause LRTI	History of cough OR difficulty breathing  AND SpO 2 < 95%  , OR RR increase 	Same but with SpO2 < 92%

LRTI = lower respiratory tract infections; RR = respiratory rate; RTI = respiratory tract infections; SpO2 = blood oxygen saturation.

Based on [[Modjarrad](#), 2016]

 Based on history reported by parents.

 The lowest value during the course of illness will be used.

 RR increase defined as:

≥ 50/min (2 to 11 months of age)

≥ 40/min (12 months of age or above)

The highest value during the course of the illness will be used.

 RSV infection confirmed on nasal swab positive for RSV A or B by quantitative Reverse Transcription Polymerase Chain Reaction (qRT-PCR).

 RSV sampling and testing is based on medical judgment of medical practitioner or driven by algorithm.

 Hospitalization is defined as a medical decision that the infant requires admission for observation or treatment.

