### 6.6.12.3. Nasal swab or other specimen for PCR assay

#### Nasal swab or other specimen for PCR assay collected during assessment visit

Real time assessment of potential RSV-LRTI cases is important for the timely monitoring of safety.

If during passive or active surveillance contact, the investigator/study staff assesses that an infant presents a potential RSV-RTI (refer to Section 9.2), a nasal swab *or* another specimen for assay will be collected during an assessment visit:

- The nasal swab will allow assessing the potential RSV infection by quantitative RT-PCR and respiratory viral panel (RVP) at sponsor laboratory.
- The specimen for local assay will allow assessing the potential RSV infection and RVP at a local routine laboratory, where available. The specimen type will depend on the assay run locally.

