#### **9.2.4. Assessment visit**

The purpose of the assessment visit is to objectively document signs and symptoms by an appropriately qualified person (i.e., medical or nursing), provide medical advice and to take a nasal swab for detection of RSV infection.

- Assessment visits may take place in the subject's home, the investigators clinical facility or a medical facility as appropriate to the circumstances in the judgment of the investigator.
- If the reported symptoms are already of a level of severity that urgent care is indicated, the parent(s)/LAR(s) should be redirected to the proper location to receive this care (e.g., Emergency Room) and an assessment visit could be scheduled to take place there at a suitable time.
- During the assessment visit, the investigator/study staff will evaluate the clinical signs and symptoms of the RTI. Signs and symptoms to be recorded in the eCRF are listed in the SPM.
- Oxygen saturation will be measured by pulse oximetry in room air using standardized equipment in preference.
- Specimen for testing of RSV and RVP at a local routine laboratory will be collected for all the subjects who have symptoms of an RTI.
- Nasal swabs for analysis at sponsor laboratory will be collected for all the subjects who have symptoms of an RTI. Note: all subjects experiencing an RSV-LRTI must be reported as an SAE in an expedited manner (refer to Section 9.4).
- Parent(s)/LAR(s) will be instructed to contact the study staff if the severity of the already existing symptoms increases or if the subject develops difficulty in breathing or wheezing and this may lead to a repeat assessment visit upon the judgment of the investigator.
- During subsequent surveillance contacts after an assessment visit, the status and evolution of the case will be followed until case resolution.
- Each assessment visit will be encoded in the eCRF.

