## APPENDIX D THE SYMPTOMS AND GRADING FOR ASSESSMENT VISITS AND WORSENING VISITS

HISTORY FROM PARENT OR CARER - PART 1			
Symptoms of RTI	Cough	Yes/No (if Yes: start date and end date)	
	Runny nose	Yes/No (if Yes: start date and end date)	
	Blocked nose	Yes/No (if Yes: start date and end date)	
	Wheezing	Yes/No (if Yes: start date and end date)	
	Difficulty in breathing	Yes/No (if Yes: start date and end date)	
Parental/Carer concern	Parental concern	Yes/No	
MEDICAL OBSERVATION - PART 2a*			
Temperature	Record temperature and route of measurement		
Heart rate	Beats per minute when child is settled		
Respiratory rate	Breaths per minute counted over one minute		
Lower chest wall indrawing (subcostal recession)	Yes/No		
SpO2	% measured in room air when quiet and not feeding (NB altitude is collected for each participating site)		
Nasal swab taken for testing at central laboratory	Yes/No		
Specimen taken for RSV and RVP testing at local laboratory	Yes/No (If Yes specify type of specimen test and result: positive/negative)		
Has a blood sample been taken for assessment of mechanism of illness?	Yes/No/ Not available		
MEDICAL OBSERVATION - PART 2b*			
Must be completed in full if:			

 
• The parent or carer reports wheezing or difficulty in breathing
 
• The respiratory rate is > 40/minute for subject 12-30 months of age
 
• Lower chest wall indrawing is observed
 
• SpO2 measured in room air by pulse oximetry is < 95%
 
			
N.B. May be completed in part or in full for any child attending an assessment visit			
Signs of increased respiratory effort	Audible wheeze	Yes/No/Not available	
	Grunting	Yes/No/Not available	
	Nasal flaring	Yes/No/Not available	
	Intercostal recession	Yes/No/Not available	
	Signs associated with severity	Apnea outside medical facility	Has an episode of apnea > 20 seconds occurred outside a medical facility? Yes/No/Not available (if Yes provide all details [free text field])
		Apnea under medical observation	Has an episode of apnea > 20 seconds occurred during medical observation? Yes/No/Not available (if Yes provide all details [free text field])
		Peripheral cyanosis	Yes/No/Not available
		Central cyanosis	Yes/No/Not available

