		Irritability/agitation	0 = content, happy, interactive 1 = mildly irritable when touched, occasional crying, can be comforted, is interactive 2 = moderately irritable, intermittently crying, resists comforting, less interactive 3 = extremely irritable, cannot be comforted, crying throughout examination or not interactive Not available
	Lethargy/excessive sleepiness	0 = interactive 1 = mildly lethargic/sleepy is normally interactive when roused 2 = moderately lethargic/ sleepy, less interactive than normal when roused 3 = extremely lethargic/sleepy, is not interactive when roused Not available	

	Conscious level	A = The child is awake, alert, and interactive with parents and care providers V = The child responds only if the care provider or parents call the child's name or speak loudly P = The child responds only to painful stimuli, such as pinching the nail bed of a toe or finger. U = The child is unresponsive to all stimuli Not available
	Assessment of feeding ability	0 = Normal feeding 1 = Reduced ability to feed 2 = Unable to feed Not available
	Skin turgor	Yes → > 2 seconds No → ≤ 2 seconds Not available
Findings on auscultation	Wheeze on auscultation with stethoscope	Yes/No/Not available
	Crackles	Yes/No/Not available
Investigations	Chest X-ray if available**	Collected? Yes/No/Not available (If Yes: specify date and specify the presence or absence of the following features: hyperexpansion, peribronchial thickening, interstitial infiltrates, segmental or lobar consolidation, pleural effusion, atelectasis, other: please specify)
	Blood culture if available**	Collected? Yes/No (If Yes, specify date and coded results as 1. Pneumococcus, 2. Haemophilus influenza 3. Meningococcus, 4. Salmonella, 5. Other pathogenic organism, 6. Contaminant, 7. No isolate, 8. No result [missing confirmed] and note if 1 to 6: was the period of incubation to positivity detection > 48 hours? Yes/No, if 1, 2, 3 or 4 specify serotype/group, if 5 or 6 specify organism and if 8 comment)

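### Appendix D Part 2b has no respiratory-rate trigger below 12 months, so two components of very severe RSV-LRTI can stay optional in infants who meet RSV-LRTI through cough and a raised rate

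*Protocol*

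**What the plan says.** Protocol Table 6 defines RSV-LRTI as a history of cough or difficulty breathing, with either low SpO2 or a raised respiratory rate, and RSV confirmed on the nasal swab. A raised rate is "≥ 50/min (2 to 11 months of age") or at least 40/min from 12 months. Very severe RSV-LRTI adds any one of three things: SpO2 below 90% (88% at high altitude), inability to feed, or unresponsiveness.

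Appendix D decides where these are recorded. Respiratory rate, SpO2 and indrawing are in Part 2a, which has no entry condition. "Assessment of feeding ability" and conscious level are in Part 2b, which is introduced by "Must be completed in full if" and four triggers:

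- "The parent or carer reports wheezing or difficulty in breathing"
- a respiratory rate above "40/minute for subject 12-30 months of age"
- "Lower chest wall indrawing is observed"
- SpO2 in room air below 95%

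If no trigger is met, Part 2b may be completed but need not be. Part 3 asks again about feeding and consciousness, but only when the investigator judges that the infant has deteriorated.

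**The concern.** The form and the case definition use different respiratory-rate rules, and the form's rule omits an age band that matters. Infants are enrolled from 6 months up to the day before 8 months (Section 5.2), so they turn 12 months roughly 4 to 6 months after Dose 1 (12 − 8 and 12 − 6). Dose 1 precedes the first RSV season, and Table 2 puts infants at 10–11 months on Day 121. Much of the first season is therefore spent under 12 months.

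That season is the window for the secondary endpoint of very severe RSV-LRTI among RSV-infected infants with negative exposure status (Section 11.2). It is the endpoint on which the sample size is built (Section 11.4). The monthly IDMC reports also use the Table 6 categories (Section 9.10.3). If feeding ability or conscious level is not recorded at the visit, the analysis cannot recover it later.

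**Working it through.** **Step 1. Compare the two rate rules.** The question is whether an infant who meets the Table 6 rate criterion also meets the Part 2b rate trigger.

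| Age (months) | Rate per minute | Table 6 rate criterion | Part 2b rate trigger |
|---|---|---|---|
| 6, 8, 11 | 50 or 60 | met | none exists |
| 12, 14 | 40 | met | not met |
| 12, 14 | 41 or more | met | met |

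Below 12 months the rate never makes Part 2b compulsory. From 12 months the only mismatch is at exactly 40/min.

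**Step 2. State who falls in the gap.** The other three triggers apply at every age, so all of these must hold: under 12 months, cough, confirmed RSV, rate of at least 50/min, SpO2 of at least 95%, no indrawing, and no parent-reported wheeze or difficulty breathing. Such an infant is an RSV-LRTI case and Part 2b is optional. A very severe case is missed only if the infant also cannot feed or is unresponsive, the page is left blank, and no other route records it. The Amendment 1 record in Appendix E shows the same four triggers, so a line lost from the appendix is unlikely.

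**Step 3. Reproduce the plan's own figure.** Section 11.4 gives 5 infections per vaccine group, one-sided alpha 0.05, a true progression rate of 10%, a null rate of 80%, at least 90% power, and a limit of 1 very severe case in 5. For X ~ Binomial(5, p):

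- Power at p = 0.10: 0.9^5 + 5 × 0.1 × 0.9^4 = 0.59049 + 0.32805 = 0.9185. The stated power is reproduced.
- Error rate at p = 0.80 for X ≤ 1: 0.2^5 + 5 × 0.8 × 0.2^4 = 0.00032 + 0.0064 = 0.0067.
- Error rate at p = 0.80 for X ≤ 2: 0.0067 + 10 × 0.64 × 0.008 = 0.0579, above 0.05. The limit of 1 in 5 is therefore right.

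**Step 4. Illustrate what one case can do.** The exact (Clopper-Pearson) one-sided 95% upper limit for x of n is the 0.95 quantile of Beta(x + 1, n − x):

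- 2/5: 81.1%, so 80% is not excluded.
- 1/5: 65.7%, so 80% is excluded.

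**Step 5. Vary an assumed capture share.** The documents do not give the share s of very severe cases that is recorded, so this is an assumption. With a true rate of 80%, the observed rate is 0.8s, and the chance of X ≤ 1 is:

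| s | Chance of wrongly excluding 80% |
|---|---|
| 1.0 | 0.7% |
| 0.9 | 2.4% |
| 0.8 | 6.0% |
| 0.7 | 12.1% |
| 0.5 | 33.7% |

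The chance passes 5% once s falls below about 0.82. Nothing in the protocol shows that this form defect alone would lower s that far.

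**The case against.** The strongest objection is that very few very severe cases could slip through, and most of it stands. SpO2 is always recorded in Part 2a, so the saturation component is safe at any age, as is classification as RSV-LRTI or severe RSV-LRTI. An infant sick enough to stop feeding or responding will often have indrawing, low SpO2 or a parent who reports laboured breathing, and any of these makes Part 2b compulsory. Part 2b may be filled in voluntarily, Part 3 captures deterioration, and Section 9.2.5 has the assessment page completed as fully as possible from records for infants hospitalised with LRTI. The Study Procedures Manual, which is not at hand, also lists the signs to record. These routes narrow the gap without closing it: they depend on judgement, admission or another sign being present. Part 3 also records change against the assessment visit, and a blank Part 2b leaves no baseline for feeding or consciousness.

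A reader might infer that every infant under 12 months with a raised rate, normal SpO2 and no indrawing escapes Part 2b. That is not so, because parent-reported wheeze or difficulty breathing is a trigger at any age.

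A reader might also see a second route to lost cases in Section 6.6.12.3, which asks for a nasal swab or "another specimen for assay will be collected during an assessment visit", while Table 6 confirms RSV only on the swab. The documents do not support that reading. Section 9.2.4 states: "Nasal swabs for analysis at sponsor laboratory will be collected for all the subjects who have symptoms of an RTI". Sections 3, 9.1.5.2 and 9.2.5 and Table 14 also call for the swab, and Section 6.6.12.3 itself goes on to describe both specimens. A missing swab would not push the result one way either: losing a mild infection turns 1/5 into 1/4 and raises the observed rate, while losing a very severe one lowers it. The wording is an editorial slip.

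**Conclusion.** The mismatch is real and should be fixed. Below 12 months, a respiratory rate that counts towards RSV-LRTI does not oblige anyone to record two of the three very severe components; from 12 months the form and Table 6 differ only at exactly 40/min, which affects a form prompt and not the classification itself.

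The gap is narrow and its size is unknown. The move from 81.1% to 65.7% assumes that there are five infections, that two are very severe, and that exactly one of those falls in the gap and goes unrecorded. It shows how little slack a five-infection rule has and is not an estimate of this defect's effect. It would be tempting to conclude that the enhanced-disease result is biased towards safety; the documents support only that a missed component, if it occurred, would lower the very severe count.

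**What to change.** Either of two changes would do.

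1. In Appendix D Part 2b, add a trigger of at least 50/min at 2–11 months and change the existing one to at least 40/min from 12 months. Since RSV-LRTI in Table 6 requires low SpO2 or a raised rate, every infant who meets it on assessment-visit values would then have Part 2b completed.
2. Record feeding ability and conscious level at every assessment visit, by moving them to Part 2a.

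The cost is a few lines of text, an eCRF check and a slightly longer form for some infants, with no new procedure.

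As an editorial correction only, reword Section 6.6.12.3 so that the central nasal swab is collected together with the local specimen, in line with Section 9.2.4.

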**Amended text has been included in *bold italics* and deleted text in ~~strikethrough~~ in the following sections:**

On the protocol cover page the other study comparator vaccines were amended.

**Other study vaccines**

- *GSK's pneumococcal polysaccharide conjugate vaccine (Synflorix)*
- GSK's meningococcal group A, C, W-135 and Y conjugate vaccine licensed to Pfizer (*Nimenrix*~~Menveo~~)
- ~~Pfizer's meningococcal group C polysaccharide conjugate vaccine (NeisVac-C)~~
- ~~Saline~~*Placebo* (Formulation buffer S9b)

The detailed title was amended.

**Detailed title**

A Phase 1/2, randomized, observer-blind, controlled, multi-center study to evaluate safety, reactogenicity and immunogenicity of GSK Biologicals' respiratory syncytial virus (RSV) investigational vaccine based on the RSV viral proteins F, N and M2-1 encoded by chimpanzee-derived adenovector (ChAd155-RSV) (GSK3389245A), when administered intramuscularly *as a single dose or as two doses* according to a 0, 1-month schedule, to infants aged 6 and 7 months.

On the protocol cover page and on the Sponsor Signatory Approval page the **Contributing authors** have been added.

Contributing authors	
 
• PPD (Clinical Research and Development Lead)
 
• PPD (Project Statistician)
 
• PPD (Study Delivery Lead)
 
• PPD (Clinical Read-out Team Leader)
 
• PPD (Clinical and Epidemiology Research and Development Project Lead)
 
• PPD (Clinical and Epidemiology Research and Development Project Lead)
 

-----------------------------	--

On the Signatory Approval page the EudraCT number was added and the **Sponsor signatory** has been replaced.

EudraCT number	2018-000431-27
Sponsor signatory	PPD, Director [name] (Clinical and Epidemiology Research & Development Project Lead)

In the **Synopsis**, the following changes have been made:

Rationale for the study and study design	
 
• Rationale for the study GSK Biologicals is developing the pediatric candidate RSV vaccine (ChAd155-RSV vaccine) to protect infants from RSV diseases.  The purpose of this study is to provide critical information on the safety, reactogenicity and immunogenicity profile of the ChAd155-RSV vaccine in infants likely to be unexposed to RSV before moving to a dose selection and a proof-of-concept trial in infants. This An important aspect of this phase I/II study will be to compare a single lower dose of <math>1.5 \times 10^{10}</math> viral particles (vp) and two higher doses of <math>5 \times 10^{10}</math> vp according to a 0, 1 month schedule administered to infants aged 6 and 7 months likely to be unexposed to RSV, which is powered to statistically exclude a level of risk of
 

---	--

~~'vaccine-induced enhanced RSV disease' after vaccination of infants aged 6 and 7 months, likely to be unexposed to RSV, associated with the ChAd155-historic FI-RSV vaccine trials.~~  
**(Amended 16 July 2018)**

- **Rationale for the study design**

**Study population:** The immunogenicity, safety and reactogenicity of the pediatric candidate RSV vaccine (ChAd155-RSV vaccine) has been evaluated in healthy adults aged 18 to 45 years (study 201974 [RSV PED-001; NCT02491463]). A clinical study is currently being conducted in RSV-seropositive infants aged 12 to 23 months (study 204838 [RSV PED-002]). The safety profile of the ChAd155-RSV vaccine in adults (study 201974 [RSV PED-001; NCT02491463]) has been evaluated **and determined to be** satisfactory by an Independent Data Monitoring Committee (IDMC). ~~At the condition of~~**Should there be a** satisfactory safety profile of the ChAd155-RSV vaccine in RSV-seropositive infants, as evaluated by an IDMC on Day 60 data (i.e., ~~Day~~ 30 days post-dose 2 of the highest dose level) of the study RSV PED-002, the present study will be performed. This study will be conducted ~~on~~ in infants aged 6 and 7 months, (having a low chance of natural exposure to RSV before inclusion in the study.). **The primary analysis for incidence of LRTI will be conducted in infants with a negative RSV exposure status (at screening based on in-stream baseline serological testing). This study will support the decision to allow age de-escalation to the targeted population (infants as from 6 weeks of age). in the subsequent study.**

**Control vaccines:** Active ~~controls~~: Active ~~controls~~**comparators** are included as a control for the reactogenicity, safety and immunogenicity assessments. The choice of one of four ~~meningococcal~~**control** vaccines, as active comparators has been driven by the fact that, in most countries at least one of these vaccines meet the criteria of being of medical benefit, and where possible licensed for infants and used with a similar dose and schedule as the investigational RSV vaccine, while not being part of a national immunization program. The choice of which active control ~~meningococcal~~-comparator vaccine ~~will~~**to** be used will be done at the country level and will be used according to its approved label.

~~To provide benefit to all trial participants and to maintain the study blind until the end of follow up, the ChAd155-RSV~~

vaccine recipients will also receive immunization with the selected meningocecal vaccine.

*A placebo group was added to accommodate a request from countries that were not able to identify a suitable active comparator.*

- ~~Regimen, dose and route of administration: A vaccination regimen based on~~

*This study will evaluate two intramuscular (IM) injections (in the anterolateral thigh) of  $5 \times 10^{10}$  viral particles (vp) regimens of the ChAd155-RSV vaccine; either one lower dose of  $1.5 \times 10^{10}$  vp or two doses of  $5 \times 10^{10}$  vp will be administered according to a 0, 1 month. For the two dose schedule (4 week, an interval of approximately one month between vaccinations) will be dosing will be used. A single dose arm was added in this 6-7 month-old study population before going to target population in subsequent studies.*

*The dose levels to be evaluated in this study*—This dose level is the same as the highest dose have previously been administered to RSV-seropositive infants aged 12 to 23 months (study RSV PED-002 [204838]) and will have been shown to have a satisfactory safety profile and reviewed by the IDMC. This dose These doses might be modified following review by the IDMC of the safety data from study RSV- PED-002 (204838). However if no significant safety concerns are identified with the highest ChAd155-RSV vaccine dose of  $5 \times 10^{10}$  vp administered in the RSV PED-002 study, ~~it~~that dose will be the highest does level evaluated in this study.

~~The 4 week interval regimen has been tested in preclinical models and results from a In the bovine RSV challenge model in which seronegative, colostrum-restricted newborn calves were vaccinated with, both a single and two doses dose regimen of  $5 \times 10^{10}$  vp ChAd155-RSV, have been evaluated. The two dose regimen was given at an interval of four weeks apart. Both regimens showed that dose regimen was immunogenic and protected calves from a similar level of protection against challenge with bovine RSV disease and infection and, but the two dose regimen showed higher immunogenicity. Neither regimen was not associated to with pulmonary pathology.~~

~~A Phase I clinical trial evaluated a simian adenoviral vector based RSV vaccine with the same insert as ChAd155-RSV candidate vaccine (PanAd3-RSV) [RSV001 Interim Study~~

~~Report, 2014]. Data from this trial, with 42 subjects, showed that a vaccination regimen based on two IM injections, separated by four weeks, was safe and immunogenic.~~

In this study, infants aged 6 and 7 months will be administered ~~with Dose 1~~ **the first dose** of the ChAd155-RSV vaccine before the RSV season to increase the probability of enrolling infants unexposed to RSV, and then followed up through the RSV season. ***The second dose will be given one month after the first dose.***

